8. STATISTICAL CONSIDERATIONS

8.1. Analysis Objectives and Endpoints

8.1.1. Analysis Objectives

The primary objective of the PK Lead-in phase is:

- To evaluate the steady state pharmacokinetics (PK) and confirm the dose of sofosbuvir/velpatasvir (SOF/VEL FDC) in pediatric subjects with chronic hepatitis C virus (HCV) infection

The primary objective of the Treatment Phase of this study is:

- To evaluate the safety and tolerability of SOF/VEL FDC for 12 weeks in pediatric subjects with chronic HCV

The secondary objective of the PK Lead-in Phase is:

- To evaluate the safety, tolerability, and antiviral activity of 7 days of dosing of SOF/VEL FDC in pediatric subjects with chronic HCV

The secondary objectives of the Treatment Phase of this study are:

- To determine the efficacy of SOF/VEL FDC for 12 weeks in pediatric subjects with chronic HCV infection, as assessed by the proportion of subjects with sustained virological response (SVR) 12 weeks after cessation of treatment (SVR12)
- To determine the proportion of subjects with SVR 4 and 24 weeks after cessation of treatment (SVR4 and SVR24)
- To evaluate the proportion of subjects with virologic failure, including breakthrough/nonresponse and relapse
- To evaluate the kinetics of circulating HCV RNA during treatment and after cessation of treatment
- To evaluate the emergence of viral resistance to SOF and VEL during treatment and after cessation of treatment
- To evaluate the effect of treatment with SOF/VEL FDC on quality of life as measured by PedsQL™ Pediatric Quality of Life survey
- To evaluate the effect of SOF/VEL on growth and development of pediatric subjects during and after treatment
- To evaluate the acceptability, including palatability, of formulations used in the study

The exploratory objective of this study is:

The logo for CCI (Child Clinical Investigations) is displayed in large, bold, red letters on a black rectangular background.

8.1.2. Primary Endpoint

The appropriateness of the SOF/VEL FDC dose will be assessed by evaluating the steady-state PK of the VEL, SOF, and GS-331007 at Day 7. Estimated PK parameters will include C_{max} , T_{max} , C_{last} , T_{last} , C_{tau} , AUC_{tau} , CL/F , Vz/F and $t_{1/2}$, as appropriate). The primary PK endpoint of the PK Lead-in Phase is AUC_{tau} of VEL, SOF, and its major metabolite (GS-331007).

The primary endpoint of the Treatment Phase is assessment of any AEs with a focus on AEs that lead to discontinuation of study drug.

8.1.3. Secondary Endpoint

The secondary endpoints of the PK Lead-in Phase are:

- Antiviral activity measurements, including assessment of HCV RNA from baseline through Day 7.
- Any AE leading to permanent discontinuation of study drug.

The secondary endpoints of the Treatment Phase are:

- The proportion of subjects with sustained virological response (SVR) 12 weeks after cessation of treatment (SVR12). SVR12 is the key efficacy endpoint.
- The proportion of subjects with HCV RNA < LLOQ at 4 or 24 weeks after cessation of treatment (SVR4 and SVR24).
- The proportion of subjects with virologic failure, including breakthrough/nonresponse and relapse
- The proportion of subjects with HCV RNA < LLOQ on treatment
- Emergence of viral resistance to SOF and /or VEL during treatment and treatment is discontinued
- HCV RNA change from Day 1
- Quality of life endpoints and neuropsychiatric assessments as measured by PedsQL™ Pediatric Quality of Life survey
- Growth and development measurements including height and weight percentiles, Tanner Stage, parental height, and bone age
- Acceptability assessed by swallowability and palatability

8.1.4. Other Endpoints of Interest

Other endpoint of interest may include ALT normalization.

8.2. Analysis Conventions

All individual subject data will be listed as measured. All statistical summaries and analyses will be performed using SAS[®] software (SAS Institute, Cary, North Carolina, USA).

The study drug in this study is SOF/VEL FDC. Last dose of the study drug refers to the last dose of SOF/VEL FDC and will be used in the definition of treatment-emergent AEs and laboratory abnormalities as well as the efficacy endpoints of SVR at various posttreatment timepoints.

8.2.1. Analysis Sets

8.2.1.1. Efficacy Analysis Set

The analysis set for antiviral activity analyses is defined as the Full Analysis Set (FAS) which includes who were enrolled into the study and took at least one dose of the study drug.

8.2.1.2. Safety Analysis Set

The primary analysis set for safety analyses will include subjects who took at least one dose of the study drug.

Treatment-emergent data will be analyzed and defined as data collected from the first dose of the study drug through the date of the last dose of the study drug plus 30 days.

8.2.1.3. Pharmacokinetics Analysis Sets

Intensive PK Lead-in Analysis Set

The intensive PK analysis set will include all PK Lead-in subjects who took at least one dose of the study drug and for whom at least one non-missing PK concentration data, during the intensive sampling period was reported by PK lab. The PK analysis set will be used for detailed pharmacokinetic analysis of VEL, SOF, or its primary metabolite(s).

PK Analysis Set

The PK analysis set will include all enrolled subjects who took at least one dose of study drug and for whom at least one observed concentration data VEL, SOF, or its primary metabolite(s) are available. The PK analysis set will be used for analysis of general PK and single sample plasma concentrations and used for Population PK analysis.

8.2.2. Data Handling Conventions

Missing data can have an impact upon the interpretation of the trial data. Other than the endpoints discussed below, in general, values for missing data will not be imputed.

For the analyses of categorical HCV RNA data, missing posttreatment HCV RNA data will have the missing data imputed. Missing on-treatment HCV RNA will have the missing data imputed up to the time of the last dose.

If a data point is missing and is preceded and followed in time by values that are “< LLOQ target not detected (TND),” then the missing data point will be set to “< LLOQ TND.” If a data point is missing and preceded and followed by values that are “< LLOQ detected,” or preceded by “< LLOQ detected” and followed by “< LLOQ TND,” or preceded by “< LLOQ TND” and followed by “< LLOQ detected,” then the missing value will be set to “< LLOQ detected.” In these situations the data point will be termed a bracketed success; otherwise, the data point will be termed a bracketed failure (i.e., \geq LLOQ detected). If a data point is missing and is not bracketed, the missing data point will also be termed a failure (i.e., \geq LLOQ detected) except for SVR24, which will be imputed according to the SVR12 status. Success for SVR12 who have no further HCV RNA measurements collected will be counted as a success for SVR24 due to the high correlation between these 2 endpoints.

Where appropriate, safety data for subjects that did not complete the study will be included in summary statistics. For example:

- If a subject received at least 1 dose of study drug, the subject will be included in a summary of adverse events according to the treatment received; otherwise, if the subject is not dosed then they will be excluded from the summary.
- If safety laboratory results for a subject are missing for any reason at a time point, the subject will be excluded from the calculation of summary statistics for that time point. If the subject is missing a predose value, then the subject will be excluded from the calculation of summary statistics for the predose value and the change from predose values.

Values for missing safety laboratory data will not be imputed; however, a missing Day 1 result will be replaced with a screening result, if available. If no pretreatment laboratory value is available, the Day 1 value will be assumed to be normal (i.e., no grade [Grade 0]) for the summary of graded laboratory abnormalities.

Values for missing vital signs data will not be imputed; however, a missing Day 1 result will be replaced with a screening result, if available.

HCV RNA values below the LLOQ for the assay will be set to the lower limit minus 1 for calculation of summary statistics for the actual HCV RNA values and the change from baseline values by study visit. The reported values will be provided in the HCV RNA listing.

For selected analyses of early time point data, HCV RNA data (IU/mL) may be transformed to the logarithmic (base 10) scale (\log_{10} IU/mL).

For PK plasma concentrations and analysis of PK parameters natural logarithmic transformation will be used. Plasma concentration values that are below the lower limit of quantitation (BLQ) will be presented as “BLQ” in the concentration data listing. Values that are BLQ will be treated as 0 at predose time points, and one-half the value of the lower limit of quantitation (LLOQ) at post baseline time points, where LLOQ is corrected for the dilution factor (i.e., reported LLOQ/dilution factor) for determination of summary and order statistics.

For the presentation of summary and order statistics, if at least 1 subject has a concentration value of BLQ for the time point, then the minimum value will be displayed as “BLQ.” If more than 25% of the subjects have a concentration data value of BLQ for a given time point, then the minimum and Q1 values will be displayed as “BLQ.” If more than 50% of the subjects have a concentration data value of BLQ for a given time point, then the minimum, Q1, and median values will be displayed as “BLQ.” If more than 75% of the subjects have a concentration data value of BLQ for a given time point, then the minimum, Q1, median, and Q3 values will be displayed as “BLQ.” If all subjects have concentration data values of BLQ for a given time point, then all order statistics (minimum, Q1, median, Q3, and maximum) and summary statistics will be displayed as “BLQ.”

8.3. Demographic Data and Baseline Characteristics

Demographic and baseline measurements will be summarized using standard descriptive methods.

Demographic data will include sex, self-identified race/ethnicity, and age.

Baseline characteristic data will include body mass index, HCV RNA level (\log_{10} IU/mL), genotype of HCV infection, IL28B genotype, and additional endpoints as necessary.

8.4. Efficacy Analysis

8.4.1. Analysis of the Key Efficacy Endpoint

The key efficacy endpoint is SVR12 on the FAS. The analysis of SVR12 will be performed after all enrolled subjects have been followed through posttreatment Week 12 or discontinued from the study. The point estimate of the SVR12 rate and the 2-sided 95% exact CIs based on Clopper-Pearson method will be calculated.

8.4.2. Secondary Analyses

The proportion of subjects with HCV RNA below the LLOQ over time (including SVR4 and SVR24) will be presented in tabular and graphical form. Descriptive summaries and listings will be provided for additional efficacy evaluations of the proportion of subjects who experience virologic failure, serum HCV RNA actual values and change from baseline, quality of life endpoints and other endpoint of interest may include ALT normalization.

Exploratory analyses may be performed to assess the relationship between demographic, baseline characteristics (including baseline viral load, genotype, age, sex, race, ethnicity, baseline ALT level), and antiviral activity (HCV RNA reduction, proportion of subjects with HCV RNA < LLOQ at various time points during and following discontinuation of active therapy).

Details on efficacy analyses will be described in the statistical analysis plan.

8.5. Safety Analysis

Safety will be evaluated by assessment of clinical laboratory tests, physical examinations, vital signs measurements at various time points during the study, and by the documentation of AEs.

All safety data collected on or after the first dose of the study drug administration up to 30 days after the last dose of the study drug will be summarized.

8.5.1. Extent of Exposure

A subject's extent of exposure to the study drug will be generated from the study drug administration page of eCRF. Exposure data will be summarized.

8.5.2. Adverse Events

Clinical and laboratory adverse events will be coded using the Medical Dictionary for Regulatory Activities (MedDRA). System Organ Class (SOC), High-Level Group Term (HLGT), High-Level Term (HLT), Preferred Term (PT), and Lower-Level Term (LLT) will be attached to the clinical database.

Events will be summarized on the basis of the date of onset for the event. A treatment-emergent adverse event will be defined as any adverse event with an onset date on or after the study drug start date and no later than 30 days after permanent discontinuation of the study drug or any adverse event leading to premature discontinuation of the study drug.

Summaries (number and percentage of subjects) of treatment-emergent adverse events (by SOC, and PT) will be provided:

- All AEs
- AEs of Grade 3 or above
- AEs of Grade 2 or above
- All treatment-related AEs
- Treatment-related AEs of Grade 3 or above
- Treatment-related AEs of Grade 2 or above

- All SAEs
- All treatment-related SAEs
- All AEs leading to premature discontinuation of the study drug

All AEs collected during the study will be presented in the data listings

8.5.3. Laboratory Evaluations

Selected laboratory data (using conventional units) will be summarized (n, mean, SD, median, Q1, Q3, minimum, and maximum) by study visit along with the corresponding change from baseline.

Graded laboratory abnormalities will be defined using the laboratory toxicity grading scheme defined in [Appendix 3](#).

Incidence of treatment-emergent laboratory abnormalities, defined as values that increase by at least one toxicity grade from baseline at any time post baseline up to and including the date of last dose of study drug plus 30 days, will be summarized.

Values for missing safety laboratory data will not be imputed; however, a missing Day 1 result will be replaced with a screening result, if available. If no pretreatment laboratory value is available, the baseline value will be assumed to be normal (i.e., no grade [Grade 0]) for the summary of graded laboratory abnormalities.

All laboratory abnormalities will be included in the listings of laboratory data.

8.5.4. Other Safety Evaluations

8.5.4.1. Tanner Pubertal Stage Assessment

Tanner Stages ([Appendix 4](#)) will be summarized by baseline Tanner Stage using frequency and percentage by gender.

8.5.4.2. Vital Signs (including Body Weight and Height)

Vital signs including body weight and height and change from baseline will be summarized at each visit.

8.5.4.3. Bone Age Assessment

Bone age will be summarized.

8.5.5. Acceptability

Acceptability of the study treatments will be evaluated by assessing swallowability of the solid dosage tablet formulations (if subject is able to swallow the tablet), evaluation of palatability of all formulations, and a questionnaire administered to subjects and their parent/legal guardian on Day 1, Week 12, and Early Termination (as applicable).

8.6. Pharmacokinetic Analysis

PK analysis will be performed for PK Lead-in using the intensive PK Lead-in analysis set. The concentration data of VEL, SOF and metabolites (GS-566500 and GS-331007) over sampling time will be listed and summarized by nominal time and cohort. Pharmacokinetic parameters (e.g., AUC_{τ} , C_{\max} , T_{\max} , C_{last} , T_{last} , C_{τ} , and $t_{1/2}$) will be listed and summarized by cohort using descriptive statistics (eg, sample size, arithmetic mean, geometric mean, % coefficient of variation, standard deviation, median, minimum, and maximum). Plasma concentrations of the analytes over time will be plotted in semi logarithmic and linear formats as mean \pm standard deviation.

To evaluate if the exposures of SOF, GS-331007 and VEL achieved in pediatric subjects of this study are similar to the exposures observed in adult subjects, SOF, GS-331007 and VEL exposure data from this study will be compared to the integrated adult data. The primary endpoint of this analysis will be evaluated by carrying out an analysis of variance (ANOVA) for log-transformed SOF, GS-331007 and VEL AUC_{τ} . The secondary endpoints of this analysis will be the C_{\max} of SOF, VEL and GS-331007 and C_{τ} of VEL. The 90% confidence intervals will be constructed for the ratio of geometric means of each PK parameters. The equivalence boundary is set as 70% to 200%.

Dose ranging studies for SOF established that a dose of 200 mg results in suboptimal exposure compared to the 400 mg dose, and no clinically significant exposure-safety relationships were observed across a broad range of GS-331007 exposure. The Phase 1 dose ranging study GS-US-281-0102 established the anti-HCV activity of VEL and the E_{\max} models indicated that subjects will experience near maximal antiviral response (99.5% of E_{\max}) at a VEL dose of 100 mg. In the Phase 2/3 population treated with SOF/VEL FDC 400/100 mg, virologic response rates were high across all HCV genotypes and quartiles of exposure for VEL, SOF and GS-331007, including for subjects with cirrhosis, with no consistent trends in exposure-efficacy or exposure-safety relationships. Given the observed safety and efficacy profile and the lack of exposure-response across all quartiles of SOF/VEL exposure, the bounds of 70-200% support identification of a clinically relevant difference in SOF, GS-331007 or VEL exposure in the pediatric population.

In all pediatric age groups, the targeted exposures for SOF, GS-331007 and VEL are the adult equivalent for which safety and efficacy has been established. Assuming similar variability for SOF, GS-331007 or VEL AUC_{τ} in the pediatric population compared to adults, the predicted 90% CIs of the geometric mean ratio (GMR) will be contained within the bounds of 70% to 200%.

In the event more than one subject in each cohort exhibits VEL, SOF, or GS-331007 AUC_{tau} exposures less than the 2.5th percentile of adult values, a dose adjustment may be required for the cohort as appropriate.

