C_{\max} (ng/mL)	560 (48.5)	259 (53.9)	215 (172, 268)

Note: preliminary data presented to 3 significant figures.

* N=20 enrolled; N=17 evaluable for PK analysis as 3 subjects received SOF/VEL FDC 400/100 mg during the PK Lead-in

** N= 982 (SOF) or 1425 (VEL) from Ph 2/3

In summary, based on preliminary data available, SOF/VEL FDC 400/100 mg administered to adolescents, and SOF/VEL FDC 200/50 mg administered to subjects 6 to <12 years of age, was safe and well tolerated, and resulted in SOF, GS-331007, and VEL exposures within the range of exposures associated with safety and efficacy in the adult Phase 2/3 SOF/VEL program. As such, the adult dose of SOF/VEL FDC 400/100 mg is considered appropriate for use in the adolescent population (12 to <18 years of age), and the reduced dose of SOF/VEL FDC 200/50 mg is considered appropriate for children 6 to <12 years of age.

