### 1.2.1. PK Lead-in Phase

The PK Lead-in Phase will evaluate and/or confirm the age appropriate SOF/VEL FDC dose by analyzing PK, safety, and antiviral activity of SOF/VEL FDC through 7 days of dosing.

At least 17 subjects will be sequentially enrolled into each of the following 3 cohorts:

- Cohort 1: 12 to < 18 years old
- Cohort 2: 6 to < 12 years old
- Cohort 3: 3 to < 6 years old

At least 6 subjects weighing  $\geq 17$  kg

At least 6 subjects weighing  $< 17$  kg

Intensive PK and safety results through Day 7 of each Cohort will be reviewed to confirm the appropriateness of the SOF/VEL FDC dose for that age group as well as to determine the age-appropriate dose to be evaluated in the PK Lead-in Phase of the next age Cohort.

Subjects enrolled in the PK Lead-in Phase will immediately enroll in the Treatment Phase as subjects complete Day 7 of PK Lead-in. Subjects will continue dosing with SOF/VEL FDC with no interruption of study drug administration until the appropriateness of the dose is confirmed by PK and safety data from the PK Lead-in Phase.

Cohort 1 subjects will receive a SOF/VEL FDC 400/100 mg adult tablet or 2 × 200/50 mg tablets (if determined necessary based on SOF/VEL swallowability assessment) once a day for 7 days with intensive PK conducted on Day 7.

Cohort 2 subjects will receive SOF/VEL FDC 200/50 mg tablets once daily. If unable to swallow the tablet formulations, the subjects will receive SOF/VEL FDC 200/50 mg oral granules (4 × 50/12.5 mg packets) for 7 days with intensive PK conducted on Day 7.

Cohort 3 subjects weighing  $\geq 17$  kg will receive SOF/VEL FDC 200/50 mg oral granules (4 × 50/12.5 mg packets) for 7 days with intensive PK conducted on Day 7. Cohort 3 subjects weighing  $< 17$  kg will receive SOF/VEL FDC 150/37.5 mg oral granules (3 × 50/12.5 mg packets) for 7 days with intensive PK conducted on Day 7.

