##### **3.1.4. Pharmacokinetic Analysis Set**

###### **Lead-in Phase PK Analysis Set**

The Lead-in Phase PK Analysis Set includes all PK Lead-in Phase subjects who received at least one dose of study drug and for whom at least one non-missing PK concentration data value is available from the PK Lead-in Phase intensive sampling. This is the primary analysis set for PK Lead-in Phase intensive PK analysis.

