### 3.2. Subject Grouping

For analyses based on the All Enrolled Analysis Set or FAS, subjects will be grouped according to the treatment to which they were enrolled. For analyses based on the Safety Analysis Set, subjects will be grouped according to the actual treatment received. The actual treatment received is defined as the enrolled treatment except for subjects who received treatment that differs from the enrolled treatment for the entire treatment duration. In this case, the actual treatment received is defined as the treatment received for the entire treatment duration.

Generally speaking, the efficacy analyses will be performed on the FAS by age group and by HCV genotype (1 [further broken down to 1a and 1b], 2, 3, 4, 5, 6, or other, as appropriate), as determined by sequencing or, if sequencing is not available, by LIPA. The primary analysis will be performed on the FAS as described in Section 6.1.

For the safety analysis, because all subjects receive SOF/VEL FDC for 12 Weeks, subjects will be summarized by age group.

For selected analyses, for example, the summary of subject enrollment and disposition, the summary of demographics and baseline characteristics, the summary of responses to the acceptability and palatability questionnaire, and the analysis of Tanner pubertal stage assessment data, please refer to the relevant sections for the detailed description of subject grouping.

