## **8. PHARMACOKINETIC ANALYSES**

### **8.1. PK Analysis in the PK Lead-in Phase (Intensive PK Analysis)**

Intensive PK Analysis will be performed using the Lead-in Phase PK Analysis Set. Concentrations of SOF, GS-331007, GS-566500 and VEL from subjects in the PK lead-in Phase over sampling time will be listed and summarized for each age cohort using descriptive statistics (n, arithmetic mean, geometric mean and its 95% confidence interval, coefficient of variation [%CV], SD, median, Q1, Q3, minimum, and maximum) by nominal time. For Cohort 1 and 2, plasma samples will be collected for PK analyses following dosing of study drugs on Day 7 at the following time points: 0 (predose), 0.5, 1, 2, 3, 4, 6, 8, and 12 hours postdose. For Cohort 3, plasma samples for PK analyses will be collected at the following time points: 0 (predose), 0.5, 1, 2, 3, 4, 8, and 12 hours postdose. PK parameters from subjects in the PK lead-in Phase for each age cohort will be summarized (e.g;  $AUC_{\tau}$ ,  $AUC_{last}$ ,  $C_{max}$ ,  $T_{max}$ ,  $C_{last}$ ,  $T_{last}$ ,  $C_{\tau}$ ,  $T_{1/2}$ , volume of distribution and clearance [CL/F], as appropriate).

SOF, GS-331007 and VEL exposures ( $AUC_{\tau}$ ,  $C_{max}$ , and  $C_{\tau}$ , if applicable) in each age cohort will be compared with SOF/VEL adult populations. The primary endpoint of this analysis will be evaluated by carrying out an analysis of variance (ANOVA) for log-transformed SOF, GS-331007 and VEL  $AUC_{\tau}$ . The secondary endpoints of this analysis will be the  $C_{max}$  of SOF, VEL and GS-331007 and  $C_{\tau}$  of VEL. The 90% confidence intervals will be constructed for the ratio of geometric means of each PK parameters.

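### The Cohort 2 adult-comparison ratio has no dose condition, so as written it can include three subjects who took twice the cohort dose

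*Protocol*

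**What the plan says.** - **The comparison.** Protocol 8.6 uses an ANOVA on log AUCtau (primary), with Cmax and VEL Ctau as secondary parameters, and 90% intervals for the geometric mean ratio against adults. It adds: "The equivalence boundary is set as 70% to 200" percent. SAP 8.1 repeats the ANOVA and intervals and makes the age cohort the unit of comparison: exposures "in each age cohort will be compared with SOF/VEL adult populations".
- **Who is in it.** Protocol 8.2.1.3: "The intensive PK analysis set will include all PK Lead-in subjects who took at least one dose of the study drug", given at least one non-missing intensive concentration. SAP 3.1.4 has the same content: "all PK Lead-in Phase subjects who received at least one dose of study drug", with the same concentration requirement. Neither definition mentions the dose taken.
- **What was done.** The planned Cohort 2 dose is 200/50 mg (Protocol 3.3.1). The footnote to Protocol Table 1-2 reads: "N=20 enrolled; N=17 evaluable for PK analysis as 3 subjects received SOF/VEL FDC 400/100 mg during the PK Lead-in". Table 1-2 covers ages 6 to <12, so these are Cohort 2 subjects on twice the cohort dose.
- **What else might cover it.** SAP 3.2 has an actual-treatment rule, but for another set: "For analyses based on the Safety Analysis Set, subjects will be grouped according to the actual treatment received". SAP 4.3 only lists subjects who took a treatment other than the one they were enrolled to.

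**The concern.** Confirming the dose is the primary objective of the lead-in, and this ratio is its formal comparison with adults. The sponsor has already treated the three subjects as unsuitable for that comparison, but the reason stands only in a table footnote and was not carried into the set definitions. An analyst who follows the SAP literally would put them back, so that a ratio presented for 200/50 mg is partly a ratio for 400/100 mg. An analyst who wants to match the reported 17-subject table would have to drop them without a prespecified rule. The error goes one way: it raises the Cohort 2 ratio for every analyte whose exposure increases with dose.

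**Working it through.** **Inputs.** From Protocol Table 1-2 and its footnotes: 20 enrolled, 17 evaluable, 3 on 400/100 mg; 982 (SOF) or 1425 (VEL) adults; and the table's last row, Cmax 560 (CV 48.5%) in children, 259 (CV 53.9%) in adults, ratio 215% (172, 268). The AUCtau rows and the analyte label of this row were not available in the text reviewed. The calculation uses 1425 adults; using 982 changes almost nothing.

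**1. Reproduce the reported row.**
- Ratio of means: 560/259 = 216%, against 215% reported.
- Log SD from the adult CV: sqrt(ln(1 + 0.539²)) = 0.505.
- Interval: 215% multiplied and divided by exp(1.646 × 0.505 × sqrt(1/n + 1/1425)). With n = 17 this gives 176 to 263; with n = 20, 178 to 259.
- The match to 172 to 268 is approximate, since the table gives arithmetic means and CVs. It is closer with 17 subjects, as the footnote says.

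**2. Log SD implied by the reported interval.** Half-width ln(268/172)/2 = 0.2217. SE = 0.2217/1.645 = 0.1348. SD = 0.1348/sqrt(1/17 + 1/1425) = 0.55.

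**3. Shift from including the three.** Let G be the geometric mean at 200/50 mg and m the exposure multiple at double dose, and assume the three would otherwise resemble the other 17. The geometric mean of all 20 is exp[(17 ln G + 3 ln(mG))/20] = G × m^(3/20).

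| Assumption | m | Factor on the ratio |
|---|---|---|
| Exposure rises with dose to the power 0.5 | 1.41 | 1.053 |
| 1.5-fold exposure | 1.5 | 1.063 |
| Dose proportionality | 2 | 1.110 |
| Exposure rises with dose to the power 1.2 | 2.30 | 1.133 |
| 2.5-fold exposure | 2.5 | 1.147 |

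Under proportionality, a ratio of 180% at the planned dose would read as 200% (180 × 1.110), and one of 63% as 70% (63 × 1.110).

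**4. Precision.** With SD 0.55 the interval factor is exp(0.2217) = 1.248 for 17 subjects, and exp(1.645 × 0.553 × sqrt(1/20 + 1/1425)) = 1.227 for 20.

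**5. The visible row, as the set is written.** 215 × 1.110 = 239%; 239/1.227 = 194 (rounded) and 239 × 1.227 = 293. So 215% (172, 268) would become 239% (194, 293). Both upper limits exceed 200%, so the reading of this row against the boundary does not change.

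**6. Where the interval's position could change.** At the same SD, an observed planned-dose ratio has its interval inside 70% to 200% when it lies between 70 × 1.248 = 87% and 200/1.248 = 160%. With the three included, the corresponding range is 70 × 1.227/1.110 = 77% to 200/(1.227 × 1.110) = 147%. This is an illustration, because the AUCtau variability is not visible.

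**The case against.** **The exclusion is already in the protocol.** The footnote states it with a reason, the SAP says it is based on the protocol, and SAP 4.3 lists wrong-treatment subjects. This stands in part: the sponsor's intention is clear. But a footnote to preliminary data is not an analysis-set rule, and the definitions that govern the final table say otherwise.

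**The three may have no intensive concentrations.** Protocol 6.3.2 bars the Day 7 intensive sampling when dosing non-compliance is found by diary or drug count, and allows rescheduling only up to Day 11. Whether that applied is not stated. The footnote gives dose, not missing samples, as the reason they were not evaluable. This stands as a condition on the finding.

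**A reader might infer that low exposure at 200/50 mg was hidden.** The documents do not support that. The protocol calls the dose appropriate (Sections 1.2.2 and 1.3) on the table that left the three out, and the one visible row points high. Protocol 8.6 also says that a dose adjustment may be required if more than one subject in a cohort has AUCtau below the adult 2.5th percentile. That rule is a count, so adding high-exposure subjects does not dilute it.

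**A reader might treat the boundary as a pass/fail gate.** Protocol 8.6 predicts that "the predicted 90% CIs of the geometric mean ratio (GMR) will be contained within the bounds of 70% to 200" percent, but no section says that a dose is rejected otherwise. The Cmax interval of 172 to 268 lay outside the boundary and the dose was still accepted. Step 6 therefore describes where an interval would fall, not a decision.

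**A reader might extend the point to Cohort 3**, where subjects under 17 kg "will receive SOF/VEL FDC 150/37.5 mg oral granules" and heavier ones receive 200/50 mg. Those are planned weight-based doses aimed at the same adult exposure (Protocol 1.3), so pooling them by age cohort is not the same fault. Nor is it a fault that SAP 8.1 does not repeat the boundary: Protocol 8.6 sets it directly after the intervals for each PK parameter.

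**Conclusion.** The point holds for Cohort 2. Followed literally, the set definitions and SAP 8.1 mix double-dosed subjects into a ratio meant to describe 200/50 mg. The bias is about 11% upward under dose proportionality and about 5% to 15% across the other assumptions shown. The result would also disagree with the 17-subject figures already in the protocol. This rests on three assumptions: the three subjects have intensive concentrations, they would otherwise resemble the rest of the cohort, and exposure rises with dose roughly as tabulated. The effect is moderate. It concerns the final report of the adult comparison, and it is no evidence that the Cohort 2 dose was wrongly chosen.

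**What to change.** Add to SAP 3.1.4 and 8.1 that the adult comparison uses subjects who received the planned dose for their cohort, in any permitted formulation, through the intensive PK day. For Cohort 2 that means 200/50 mg; for Cohort 3, the dose planned for the subject's weight band. List the three Cohort 2 subjects on 400/100 mg separately with whatever PK data they have, and give the all-subjects ratio as a sensitivity analysis. Record this as a clarification of the set in Protocol 8.2.1.3. If the SAP is already final, document it in the clinical study report, as SAP Section 1 provides.

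The cost is a few sentences, one listing and one extra table column, with no new data. Cohort 2 then rests on 17 rather than 20 subjects, so the interval factor is about 1.25 instead of 1.23 at the implied log SD of 0.55.
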